
Study Treatment
	
Phase 1:
 
In the dose finding portion of the study, up to two cohorts may be explored and ibrutinib dose escalation will follow the 3+3+3 design for MTD/MAD and the Phase 2b dose determination.
 
Ibrutinib will be administered orally daily at a designated dose and will be initiated on Day 1 of the first cycle. The starting dose will be that of Cohort 1 (560 mg). Treatment will be continuous (without interruption) until disease progression or unacceptable toxicity. Pomalidomide 4 mg will be administered orally daily on Days 1-21 of each 28-day (4 weeks) cycle until disease progression or unacceptable toxicity. Dexamethasone will be administered orally (PO) once weekly at an age-adjusted dose of either 40 mg or 20 mg on Days 1, 8, 15 and 22 of each 28-day (4 weeks) cycle until disease progression or unacceptable toxicity.
 
  
 	Ibrutinib (PO)	Pomalidomide (PO)	Dexamethasone (PO)[†]	
   
 Cohort -1 (Dose Level -1)	420 mg	4 mg	40 mg	
 
 Cohort 1 (Dose Level 1-) Starting Dose level	560 mg	4 mg	40 mg	
 
 Cohort 2 (Dose Level 2)	840 mg	4 mg	40 mg	
  
 
[†] Dose will be 20mg weekly in those >75 years of age
 
After the MTD/MAD of ibrutinib is defined and the Phase 2b dose determined, enrollment into Phase 2b will commence. In the event that Cohort -1 will be considered the Phase 2b dose, the Sponsor may choose not to continue with Phase 2b enrollment as outlined in the protocol.
 
Phase 2b:
 
Phase 2b will be conducted as a randomized, double-blind, international, multicenter study. Eligible subjects will be randomized in a 1:1 ratio into 2 arms to receive either ibrutinib in combination with pomalidomide and dexamethasone (Treatment Arm A) or placebo in combination with
		Ibrutinib (PO)	Pomalidomide (PO)	Dexamethasone (PO)[†]	Cohort -1 (Dose Level -1)	420 mg	4 mg	40 mg	Cohort 1 (Dose Level 1-) Starting Dose level	560 mg	4 mg	40 mg	Cohort 2 (Dose Level 2)	840 mg	4 mg	40 mg
	Ibrutinib (PO)	Pomalidomide (PO)	Dexamethasone (PO)[†]														
Cohort -1 (Dose Level -1)	420 mg	4 mg	40 mg														
Cohort 1 (Dose Level 1-) Starting Dose level	560 mg	4 mg	40 mg														
Cohort 2 (Dose Level 2)	840 mg	4 mg	40 mg														

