5. TREATMENT OF SUBJECTS

5.1. Phase 1 Dose Escalation and Stopping Rules

Phase 1 will follow a 3+3+3 dose escalation design with 3-9 subjects treated at each dose level. Before determining the Phase 2b dose, at least 6 subjects will be treated at the MTD or highest dose level tested. The DLT observation period includes Cycle 1 and all pre-dose assessments per protocol on Day 1 of Cycle 2. The dose will be selected as the Phase 2b dose if the subject incidence of DLTs during the DLT observation of study treatment is <33% (ie, $\leq 1/6$ or $\leq 2/9$ subjects with a DLT). If there are ≥ 3 subjects with a DLT in Cohort 1, then the next lower dose level (Cohort -1) will be enrolled. In the event that Cohort -1 will be considered the Phase 2b dose, the Sponsor may choose not to continue with Phase 2b enrollment as outlined in the protocol (for dose levels, see [Table 1](#)).

Dose Escalation: A minimum of three subjects will be enrolled within each cohort. The DMC will evaluate each individual cohort prior to any dose escalation or de-escalation ([Table 1](#)). Before applying the dose escalation rules, 3 subjects must have completed the first cycle of therapy and have been evaluated for toxicity as defined by the DLT observation period. If no DLT is observed in the first three subjects, then dose escalation will take place. If one of three subjects experience a study treatment-related DLT during the first treatment cycle, the same cohort will be expanded to six subjects, and if two of the six experience a DLT it will be expanded to 9 subjects. If 1/6 or 2/9 subjects experiences a study treatment related DLT during the first treatment cycle, dose escalation will occur and the next cohort may be enrolled. If at any time during a cohort, ≥ 3 subjects experience a study treatment related DLT, the MTD will have been exceeded, and additional enrollment within the cohort will cease. If there are 3 DLTs in Cohort 1, Cohort -1 will be enrolled. The MTD will be defined as the highest dose cohort at which <33% of subjects in a cohort experience a study treatment related DLT. If the MTD is not reached, the maximum administered dose (MAD) will be established as the highest dose level tested per protocol.

Table 1: Dosing Levels and Cohorts

Dose Level	Cohort	Ibrutinib ^a	Pomalidomide ^b	Dexamethasone ^c
-1	-1	420 mg once daily	4 mg	40 mg
1 (Starting Dose)	1	560 mg once daily	4 mg	40 mg
2	2	840 mg once daily	4 mg	40 mg

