5.4.4. Dose Modification of Ibrutinib or Placebo

The dose of ibrutinib or placebo should be modified according to the dose modification guidelines in Table 4 if any of the following toxicities occur:

- Grade 4 neutropenia (ANC <500/ μ L) for more than 7 days. Refer to Section 6 for instruction regarding the use of growth factor support
- Grade 3 thrombocytopenia (platelets <50,000/ μ L) in the presence of clinically significant bleeding events
- Grade 4 thrombocytopenia (platelets <25,000/ μ L)
- Grade 3 or 4 nausea, vomiting, or diarrhea if persistent, despite optimal anti-emetic and/or anti-diarrheal therapy
- Any other Grade 4 or unmanageable Grade 3 toxicity attributed to ibrutinib or placebo

For Grade 3 or 4 atrial fibrillation or persistent atrial fibrillation of any grade, consider the risks and benefits of ibrutinib or placebo treatment.

If clinically indicated, the use of anticoagulants or antiplatelet agents may be considered for the thromboprophylaxis of atrial fibrillation (Section 6.1.2.4).

Table 2: Ibrutinib or Placebo Dose Modification Guidance

Hematologic Adverse Events	
Occurrence	Action to be Taken
First	Withhold ibrutinib or placebo until recovery to an ANC $\geq 750 \mu\text{L}$ or platelets $> 25,000 \mu\text{L}$ with no evidence of Grade ≥ 2 bleeding; may restart at original dose level
Subsequent ^a	Withhold ibrutinib or placebo until recovery to an ANC $\geq 750 \mu\text{L}$ or platelets $> 25,000 \mu\text{L}$ with no evidence of Grade ≥ 2 bleeding; may restart at 1 dose level lower (refer to Table 3)
Non-Hematologic Adverse Events	
Occurrence	Action to be Taken
First	Withhold ibrutinib or placebo until recovery to Grade ≤ 1 or baseline; may restart at original dose level
Subsequent ^a	Withhold ibrutinib or placebo until recovery to Grade ≤ 1 or baseline; may restart at 1 dose level lower (refer to Table 3)

^a Do not dose below 280 mg daily

Table 3: Ibrutinib or Placebo Dose Modifications

Starting Dose Level	840 mg	560 mg	420 mg
Dose Reduction Level 1	700 mg	420 mg	280 mg
Dose Reduction Level 2	560 mg	280 mg	140 mg
Dose Reduction Level 3	420 mg	Discontinue	Discontinue
Dose Reduction Level 4	280 mg	NA	NA
Dose Reduction Level 5	Discontinue	NA	NA

For required dose modification for hepatic impairment refer to Section 5.4.5 and for concomitant treatment with CYP3A inhibitors refer to [Section 6.1.2.1](#).

If ibrutinib or placebo is discontinued for toxicity, subject will end the Treatment Phase of the study.

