5.4.5. Dose Modification for Hepatic Impaired Subjects

Ibrutinib is metabolized in the liver and therefore subjects with clinically significant chronic hepatic impairment at the time of Screening (Child-Pugh class B or C) are excluded from study participation. Refer to [Appendix 10](#) for Child-Pugh classification.

- For subjects who develop mild liver impairment (Child-Pugh class A), the recommended dose for ibrutinib or placebo is 280 mg daily (two capsules)
- For subjects who develop moderate liver impairment (Child-Pugh class B), the recommended dose is 140 mg daily (one capsule).
- Subjects who develop severe hepatic impairment (Child-Pugh class C) must hold ibrutinib or placebo until resolved to moderate impairment (Child-Pugh class B) or

better, and could be re-treated according to resolved hepatic conditions (ie, 140 mg or 280 mg for moderate or mild impairment, respectively).

Subjects who develop acute hepatic toxicity with liver enzymes Grade 3 or higher while on study should be managed per standard dose modification guidelines in [Section 5.4.4](#).

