1 INTRODUCTION

The Study PCYC-1138-CA consisted of a Phase 1 and a Phase 2 part. After completion of the Phase 1 part, in which 11 subjects received study treatment, the sponsor decided to not pursue an indication for treatment of patients with multiple myeloma with ibrutinib and therefore terminate the study early. Thus, this statistical analysis plan (SAP) is to define only the key study elements for the Phase 1 part of the study including variable definitions, and statistical methods for analysis of data in evaluation of efficacy and safety. Analyses of pharmacokinetics data will be addressed in a separate document. Biomarker analysis will not be performed due to early termination of the study. Throughout this SAP, “study treatment” and “study drug” are used interchangeably.

Analysis methods specified in this document take precedence over those described in the study protocol should there be any difference.

1.1 Study Design – Phase 1

The Phase 1 part of the study was an open-label, international, multicenter dose-finding study of the ibrutinib, pomalidomide and dexamethasone combination in subjects with relapsed/refractory multiple myeloma (MM). Up to 18 patients were to be enrolled in order to determine the maximum therapeutic dose/maximum administered dose (MTD/MAD). In the dose finding portion of the study, up to 2 cohorts were to be explored (Table 1). The study followed a 3+3+3 dose escalation design. The MTD/MAD was defined as the highest dose level at which <33% (ie, ≤ 1 of 6 or ≤ 2 of 9) of subjects in a cohort experience a study treatment related dose limiting toxicity (DLT).

Table 1: Dosing Levels and Cohorts

Dose Level	Cohort	Ibrutinib ^a	Pomalidomide ^b	Dexamethasone ^c
-1	-1	420 mg once daily	4 mg	40 mg
1 (Starting Dose)	1	560 mg once daily	4 mg	40 mg
2	2	840 mg once daily	4 mg	40 mg

^a. Ibrutinib was administered PO starting on Day 1 of Cycle 1, dosing was continuous thereafter (without interruption).

^b. Pomalidomide was administered PO on Days 1 – 21 of a 28-day cycle.

^c. Dexamethasone was administered PO once weekly. The dose was reduced to 20 mg weekly in those >75 years of age

1.2 Objective/Endpoints of Study – Phase 1

- **Primary Objective**

- To determine the MTD)/ MAD of the ibrutinib, pomalidomide and dexamethasone combination.
- To determine the safety and tolerability of ibrutinib in combination with pomalidomide and dexamethasone in subjects with relapsed/refractory MM.

- **Secondary Endpoints**

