6 CHANGES IN PROTOCOL PLANNED ANALYSIS

The following modifications to the protocol “Statistical Methods and Analysis” section is made due to the decision by sponsor to terminate the study early.

- 1) Phase 2 part of the study was not initiated, therefore, the analysis for Phase 2 will not be performed.
- 2) Biomarker analysis will not be performed due to early termination of the study.
- 3) The secondary endpoint of the duration of clinical benefit response will not be performed due to the early termination of the study.

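### Protocol 5.4.4 contradicts itself for a 420 mg start: Table 2 sets a 280 mg daily floor for ibrutinib or placebo, and Table 3 lists a 140 mg step

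*Protocol*

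**What the plan says.** Table 2 in Protocol 5.4.4 gives the action after ibrutinib or placebo toxicity. After a first event the drug is held and may be restarted at the original dose. After a later event, hematologic or non-hematologic, the drug is held and the subject "may restart at 1 dose level lower (refer to Table 3". Both of these Subsequent rows carry footnote a: "Do not dose below 280 mg daily".

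The table they cite, "Table 3: Ibrutinib or Placebo Dose Modifications", has three columns, one per starting dose. The 420 mg column runs 280 mg, 140 mg, discontinue. Section 5.4.4 closes by saying that a subject whose ibrutinib or placebo is discontinued for toxicity ends the Treatment Phase.

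The 420 mg starting dose is Cohort -1 in Table 1 of Protocol 5.1. It is conditional: "If there are 3 DLTs in Cohort 1, Cohort -1 will be enrolled". The synopsis adds: "In the event that Cohort -1 will be considered the Phase 2b dose, the Sponsor may choose not to continue with Phase 2b enrollment".

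Three smaller points lie nearby:

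- The lead-in to 5.4.4 refers ibrutinib or placebo modifications to Table 4, which is the pomalidomide toxicity table in 5.5.6.
- Section 5.5.4 refers pomalidomide modifications to 5.4.5, which is the ibrutinib hepatic section.
- Section 5.4.5 describes the hepatic exclusion thus: "subjects with clinically significant chronic hepatic impairment at the time of Screening (Child-Pugh class B or C) are excluded from study participation". Exclusion 17 and the synopsis instead set the threshold at mild or worse by Child-Pugh.

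**The concern.** A footnote that sets a minimum dose and a table that goes below it, where the first directly invokes the second, leave the site without a single instruction. Take a subject who started at 420 mg and has already been reduced to 280 mg. At the next qualifying toxicity the Table 3 column offers 140 mg. The footnote rules that out and does not say what to do in its place. If the answer is discontinuation, the subject leaves the Treatment Phase; if it is 140 mg, the subject stays. Two sites could treat the same event differently, and each could claim to follow the protocol.

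This is a matter of safety instruction and consistent conduct. Analytically it could reach only the descriptive Phase 1 summaries: treatment duration (SAP 3.4), and adverse events leading to dose reduction or discontinuation (SAP 5, Table 3).

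**Working it through.** The plan states no figure to reproduce here. The check sets the two tables side by side.

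**Inputs** (Protocol 5.4.4): floor of 280 mg daily (Table 2, footnote a); reduction doses from Table 3.

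| Starting dose | Table 3 steps, in order | Lowest dose listed | Respects 280 mg floor? |
|---|---|---|---|
| 840 mg | 700, 560, 420, 280, discontinue | 280 mg | Yes |
| 560 mg | 420, 280, discontinue | 280 mg | Yes |
| 420 mg | 280, 140, discontinue | 140 mg | No |

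Reduction doses listed: 4 + 2 + 2 = 8. Below 280 mg: 1, the 140 mg entry, which is 280 - 140 = 140 mg under the floor. The other two columns go from 280 mg straight to discontinuation, so the mismatch is confined to one cell.

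**When the conflict is reached from 420 mg**, assuming that reductions accumulate:

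- First qualifying event: hold, then restart at 420 mg.
- Second: hold, then 280 mg.
- Third: Table 3 gives 140 mg; the footnote forbids it.

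The third event is the earliest point. It can come later if hematologic and non-hematologic events are each counted in their own rows.

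**Do other 140 mg rules explain the cell?** Section 5.4.5 gives 140 mg for moderate hepatic impairment that develops on study. Section 6.1.2.1 gives 140 mg with strong CYP3A inhibitors, and with moderate ones for subjects on less than 840 mg. Section 5.4.4 cross-refers to both separately, after Table 3. Table 3 itself is the toxicity ladder that Table 2 invokes, so those rules do not account for the entry.

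**Did anyone start at 420 mg?** The synopsis plans 9 to 18 subjects in Phase 1. The SAP introduction describes a completed Phase 1 "in which 11 subjects received study treatment", and 11 lies within 9 to 18. The total does not identify the path. Two hypothetical examples that obey Protocol 5.1, including its minimum of 6 subjects at the MTD or highest dose tested:

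- Cohort 1 stops at its third DLT in the fifth subject, and 6 are then treated in Cohort -1: 5 + 6 = 11.
- Cohort 1 expands to 6 with one DLT, and Cohort 2 then stops at its third DLT in the fifth subject: 6 + 5 = 11.

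The documents therefore leave open whether Cohort -1 opened. SAP 6 records that the "Phase 2 part of the study was not initiated".

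**The case against.** The best defence is structural. Footnote a sits on the very rows that invoke Table 3, and those rows are permissive, so the footnote can be read as a local limit on what Table 3 may supply. That gives a site something to argue from. It does not settle the matter: on that reading the 140 mg entry could never be used, yet Table 3 places discontinuation only after it, and the footnote names no action once 280 mg has been reached.

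The second defence is reach, and it stands as a limit on size. One cell is affected, in a cohort that opens only if Cohort 1 proves too toxic, and only from a third qualifying event. The sponsor could also decline Phase 2b at that dose.

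A reader might infer a second, equally serious contradiction: that 5.4.5 lets in subjects with Child-Pugh class A impairment whom exclusion 17 keeps out. The documents do not support this.

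- Section 5.4.5 says that class B or C is excluded, which is also true under exclusion 17. It nowhere admits class A, and its dosing bullets concern impairment that develops on study.
- Eligibility is documented against Section 4, with approval by the Medical Monitor or sponsor designee (7.1.2).
- The score in Appendix 10 has five measures of at least 1 point each, so its minimum is 5 × 1 = 5, already class A. Class A alone cannot mark the boundary without excluding everyone. The limiting condition is clinically significant impairment, which both passages contain, although one adds that it be currently active and the other that it be chronic.

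What remains is a wording mismatch.

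**Conclusion.** The contradiction within Protocol 5.4.4 is real and should be corrected. It concerns one of eight reduction doses, in one of three starting-dose columns, and applies only to subjects starting at 420 mg. For them it can decide whether study treatment continues. The conclusion rests on the text of Tables 2 and 3 alone. The third-event timing rests on the stated assumption that reductions accumulate.

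No sample size, power or alpha figure depends on it. Nor do the documents show that any subject received conflicting instructions: they do not say whether Cohort -1 opened, and the randomized part never started. A reader who inferred that the Phase 1 results are compromised would be going beyond the evidence.

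The two wrong cross-references are clerical. The one in 5.4.4 does little harm, because Tables 2 and 3 follow directly. The hepatic wording is a minor note only. No view is taken here on which dose or rule is correct.

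**What to change.** Reconcile footnote a of Table 2 with the 420 mg column of Table 3, so that a subject at 280 mg has one stated action at the next qualifying event. The sponsor's clinical team decides the content.

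In the same amendment:

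- In 5.4.4, change the reference from Table 4 to Tables 2 and 3.
- In 5.5.4, change the reference from 5.4.5 to 5.5.5 and 5.5.6.
- As a wording note, align the description of the hepatic exclusion in 5.4.5 with exclusion 17 and the synopsis. Section 4 remains the operative eligibility source.

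The cost is text correction in one amendment, with no added procedures and no change to the analysis. Because the SAP records early termination, the study report could also state whether Cohort -1 opened and, if any subject there reached this point, what was done.

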5.4.5. Dose Modification for Hepatic Impaired Subjects

Ibrutinib is metabolized in the liver and therefore subjects with clinically significant chronic hepatic impairment at the time of Screening (Child-Pugh class B or C) are excluded from study participation. Refer to [Appendix 10](#) for Child-Pugh classification.

- For subjects who develop mild liver impairment (Child-Pugh class A), the recommended dose for ibrutinib or placebo is 280 mg daily (two capsules)
- For subjects who develop moderate liver impairment (Child-Pugh class B), the recommended dose is 140 mg daily (one capsule).
- Subjects who develop severe hepatic impairment (Child-Pugh class C) must hold ibrutinib or placebo until resolved to moderate impairment (Child-Pugh class B) or

better, and could be re-treated according to resolved hepatic conditions (ie, 140 mg or 280 mg for moderate or mild impairment, respectively).

Subjects who develop acute hepatic toxicity with liver enzymes Grade 3 or higher while on study should be managed per standard dose modification guidelines in [Section 5.4.4](#).

5.5. Pomalidomide

All subjects in both phases of this study will receive pomalidomide and will follow guidelines for pomalidomide dosing and toxicity management.

Ex-US: Pomalidomide and Dexamethasone are considered standard of care for patients with Relapsed/Refractory Multiple Myeloma. Pomalidomide and Dexamethasone as standard of care background therapy will be administered to all patients participating in this trial as per the EU guidelines. Please reference [Section 5.6](#) for additional information regarding Dexamethasone.

5.5.1. Formulation, Packaging, and Storage of Pomalidomide

Pomalidomide will be shipped to the pharmacy at the study site or to the subject directly in individual bottles or blister packs. Bottles or blister packs will contain a sufficient number of capsules to last for one cycle of dosing. Pomalidomide must be dispensed in the original packaging with the label clearly visible. **Only enough pomalidomide for 1 cycle of therapy may be provided to the subject each cycle.**

Pomalidomide will be available in strengths of 4 mg, 3 mg, 2 mg and 1 mg capsules and appropriate dose will be prescribed per protocol with modifications for toxicity.

Ex-US: Commercially available Pomalidomide will be supplied as capsules for oral administration by Pharmacyclics LLC via Celgene Corporation. The commercial material will be relabeled for clinical trial use.

The Investigator or designee is responsible for taking an inventory of each shipment of pomalidomide received on the drug accountability form.

Pomalidomide should be stored at room temperature away from direct sunlight and protected from excessive heat and cold.

5.5.2. Pomalidomide Prescribing Information (Applies to US/Canada Sites Only)

Pomalidomide will be provided to research subjects in the US for the duration of their participation in this study through their insurance provider. Pomalidomide will be provided to research subjects in Canada for the duration of their participation in this study at no charge to them or their insurance providers. Pomalidomide will be provided in accordance with the POMALYST REMS™ or RevAid® program of Celgene Corporation as appropriate for the country in which drug is being used. Per standard POMALYST REMS™ or RevAid® program requirements, all physicians who prescribe pomalidomide for research subjects enrolled into this study, and all research subjects enrolled into this study, must be registered in and must comply

with all requirements of the POMALYST REMS™ or RevAid® program. Prescriptions must be filled within 7 days for females of childbearing potential and 14 days for all other risk categories. Drug will be shipped on a per subject basis by the contract pharmacy to either the clinic site or the subject directly. Only enough pomalidomide for one cycle of therapy will be supplied to the subject each cycle.

5.5.3. Pomalidomide Drug Dispensing Requirements (Applies to Ex-US Sites Only)

In investigational studies, pomalidomide will be dispensed through a qualified healthcare professional (including but not limited to nurses, pharmacists and physicians). These healthcare professionals will be trained by Celgene in requirements specific to counseling of subjects. Each site is required to have two trained counselors at all times. Once trained, these healthcare staff will counsel subjects prior to medication being dispensed to ensure that the subject has complied with all requirements including use of birth control and pregnancy testing (FCBP) and that the subject understands the risks associated with pomalidomide. This step will be documented with a completed Education and Counseling Guidance Document ([Appendix 8](#)), and no drug will be dispensed until this step occurs. Counseling includes verification with the subject that required pregnancy testing was performed and results were negative. A pomalidomide Information Sheet ([Appendix 8](#)) will be supplied with each medication dispense.

Pregnancy Testing

Pregnancy tests for females of childbearing potential. A FCBP is a female who: 1) has achieved menarche at some point; or 2) has not undergone a hysterectomy or bilateral oophorectomy; or 3) has not been naturally postmenopausal (amenorrhea following cancer therapy does not rule out childbearing potential) for at least 24 consecutive months (ie, has had menses at any time in the preceding 24 consecutive months).

Pregnancy tests must occur within 10–14 days and again within 24 hours prior to initiation of Cycle 1 of pomalidomide. FCBP with regular or no menstruation must have a pregnancy test weekly for the first 28 days and then every 28 days while on pomalidomide therapy (including breaks in therapy); at discontinuation of pomalidomide and at Day 28 post the last dose of pomalidomide. A FCBP with irregular menstruation must have a pregnancy test weekly for the first 28 days and then every 14 days while on pomalidomide therapy (including breaks in therapy), at discontinuation of pomalidomide and at Day 14 and Day 28 post the last dose of pomalidomide ([Appendix 8](#)).

Counseling

All subjects must be counseled about pregnancy precautions, risks of fetal exposure and other risks. The counseling must be done on Day 1 of each cycle (or at a minimum of every 28 days) throughout the entire duration of pomalidomide treatment, including dose interruptions, and at pomalidomide discontinuation. The Education and Counseling Guidance Document must be completed by a trained counselor ([Appendix 8](#)).

